6.2. Secondary Efficacy Analyses

Descriptive summary for observed and CFB will be provided by treatment and visit for each endpoint. Refer to Bladder Diary related parameter derivations in [Section 4.3.1](#) and average IPSS Storage score in [Section 4.3.2.1](#).

The following secondary efficacy endpoints will be analyzed based on the FAS:

- CFB to Week 12 in the average number of nocturia episodes per day
- CFB to Week 12 in the International Prostate Symptom Score (IPSS) Storage score (1-week recall)

- CFB to Week 12 in the average volume voided per micturition

The following secondary efficacy endpoint will be analyzed based on the FAS-I:

- CFB to Week 12 in the average number of daily urge urinary incontinence episodes for subjects with urinary incontinence at baseline

All four secondary endpoints will be analyzed and presented similarly as described in the primary analysis of co-primary efficacy endpoints in Section 6.1.1. The same MMRM model used for the CFB to Week 12 in average number of daily urgency episodes will be applied to all secondary endpoints except for CFB to Week 12 in the average number of daily urge urinary incontinence episodes. For this incontinence endpoint, the baseline urinary incontinence (yes vs. no) strata will not be fitted in the MMRM model.

As described in Section 4.1.2, a hierarchical gate-keeping procedure will be used to claim statistical significance for the secondary efficacy endpoints sequentially if statistical significance is achieved at the 0.05 level for both co-primary endpoints.

6.3. Other/Exploratory Endpoints

Refer to diary related parameter derivations in Section 4.3.1 and quality of life related parameters in Section 4.3.2. These analyses will be based on FAS, unless stated otherwise.

6.3.1. Efficacy

The CFB at Weeks 4, 8, 16 (where collected), 20, and 24 for all primary and secondary efficacy variables will be included into the MMRM models along with Week 12 data as described in Sections 6.1 and 6.2. The additional continuous exploratory endpoints will be summarized descriptively.

- CFB to Weeks 4, 8, 12, 20, and 24 in the IPSS total score and IPSS Quality of Life, Storage, and Voiding scores (FAS)
- CFB to Weeks 2, 4, 8, 12, 16, 20, and 24 in the average number of total daily incontinence episodes per day for subjects with urinary incontinence at baseline (FAS-I)

The number and percentage of responders and non-responders for the following exploratory endpoints will be tabulated by treatment and visit.

- Urgency episodes 50% responder (exploratory) at Weeks 4, 8, 12, 16, 20, and 24
- Urgency urinary incontinence (UUI) episodes 75% responder (exploratory) at Weeks 4, 8, 12, 16, 20, and 24

The treatment comparison of responder will use a Cochran-Mantel-Haenszel (CMH) common risk difference estimate stratified by appropriate strata per randomization stratification [6] with weights proposed by Greenland and Robins [7], which is calculated as follows. For the urgency episode responder analysis, the strata groups include baseline average micturition episodes per day (≤ 12 vs > 12), alpha blocker use with or without 5-ARI (with or without) and urinary

Incontinence (yes or no). For the incontinence responder analysis, urinary Incontinence (yes or no) will not be included in.

$$\hat{\delta}_{MH} = \frac{\sum_{i=1}^u w_i \cdot \hat{\delta}_i}{\sum_{i=1}^u w_i}, \text{ where}$$

$\hat{\delta}_i = \frac{x_i}{n_i} - \frac{y_i}{m_i}$ denotes the risk difference in stratum $i, i = 1, \dots, u$

$w_i = \frac{n_i \cdot m_i}{n_i + m_i}$ denotes the weight of stratum $i, i = 1, \dots, u$

x_i denotes the number of subjects with event in treatment₁ in stratum $i, i = 1, \dots, u$

y_i denotes the number of subjects with event in treatment₂ in stratum $i, i = 1, \dots, u$

n_i denotes the number of subjects on treatment₁ in stratum $i, i = 1, \dots, u$

m_i denotes the number of subjects on treatment₂ in stratum $i, i = 1, \dots, u$

The estimated variance of $\hat{\delta}_{MH}$ is calculated as:

$$\widehat{var}(\hat{\delta}_{MH}) = \frac{\sum_{i=1}^u L_i}{(\sum_{i=1}^u w_i)^2}$$

$$\text{where } L_i = \frac{x_i(n_i - x_i) m_i^3 + y_i(m_i - y_i) n_i^3}{n_i \cdot m_i \cdot (n_i + m_i)^2}, i = 1, \dots, u$$

Assuming a normal distribution of $\hat{\delta}_{MH}$, an approximate 95% CI is given as follows, where $z_{0.975}$ is the 97.5% quantile of the standard normal distribution:

$$CI = \left[\hat{\delta}_{MH} \pm z_{0.975} \cdot \sqrt{\widehat{var}(\hat{\delta}_{MH})} \right]$$

Also, the approximate p-value can be calculated using the following:

$$p\text{-value} = 2 \cdot \Pr \left[Z > \left| \frac{\hat{\delta}_{MH}}{\sqrt{\widehat{var}(\hat{\delta}_{MH})}} \right| \right], \text{ where } Z \sim N(0, 1)$$

If there is a stratum for a treatment group that has 0 subjects in it, the 0 count will be replaced by 0.5 in order to prevent dividing by 0 in the above equations, as suggested in Greenland and Robins.

The estimated common risk difference, and associated p-value and 2-sided 95% confidence interval will be tabulated.

6.3.2. Quality of Life

The FAS will be the analysis population for the PRO data unless stated otherwise.

6.3.2.1. CFB in [REDACTED] Scores

The questionnaire is assessed at baseline, Week 12 and Week 24. The derivation of [REDACTED] scores for Symptom Bother, Coping, Concern, Sleep, Social Interaction and total HRQL are detailed in Section 4.3.2.2. These derived scores and CFB will be descriptively summarized by treatment and visit.

6.3.2.2. [REDACTED]

[REDACTED] questionnaire is assessed at baseline, Week 12 and Week 24. The 5 questions related to mobility, self-care, usual activities, pain/discomfort and anxiety/depression will be summarized descriptively as categorical variables by treatment and visit. Each domain includes 5 level answers: no problems, slight problems, moderate problems, severe problems and extreme problems. At Week 12 and Week 24 the Pareto Classification of Health Change will be presented relative to baseline (better, worse, same, or mixed). The mapped Crosswalk index value and change from baseline will be summarized as a continuous variable by treatment and visit.

Observed VAS value, change from baseline and percent change from baseline will be summarized as a continuous variable by treatment and visit.

6.3.2.3. Patient Global Impression Scores

The questionnaire is assessed at baseline, Week 4, Week 12 and Week 24. The Patient Global Impression (PGI) questions are designed to assess a subject's overall impression of OAB in 5 categories: [REDACTED]

Each of the responses to the PGI questions will be assigned a numerical value starting from 1. A higher score represents worse outcome in each category.

Table 7: PGI Scoring

PGI Category	Score
PGI-[REDACTED]	1 = None 2 = Mild 3 = Moderate 4 = Severe
PGI-[REDACTED]	1 = Complete control 2 = A lot of control 3 = Some control 4 = Only a little control 5 = No control

PGI Category	Score
PGI-[REDACTED] PGI-[REDACTED]	1 = Never 2 = Rarely 3 = Sometimes 4 = Often 5 = Very often
PGI-[REDACTED]	1 = Much better 2 = Moderately better 3 = A little better 4 = No change 5 = A little worse 6 = Moderately worse 7 = Much worse

The questions PGI-[REDACTED], PGI-[REDACTED], PGI-[REDACTED] and PGI-[REDACTED] ordinal assessments going from lower impact of disease with score of ranging from 1 to 4 for [REDACTED] and 1 to highest impact of disease with score of 5 for PGI-[REDACTED], PGI-[REDACTED] and PGI-[REDACTED]. These questions will be summarized descriptively as numerical variables of score and change from baseline by treatment and visit. Additionally, these questions will be analyzed as categorical variables with count and percent for each category by treatment and visit.

The PGI-[REDACTED] question is asked relative to baseline. The score will only be summarized as a categorical variable with count and percent for each category by treatment and visit.

The FAS will be the analysis set for all categories except for PGI-[REDACTED]. The FAS-I will be the analysis set for the PGI-[REDACTED] analysis.

6.3.2.4. International Index of Erectile Function

The questionnaire is assessed at baseline, Week 4 and Week 24. The sum of scores and CFB for each of 4 main domains of male sexual function: erectile function, orgasmic function, sexual desire and intercourse satisfaction plus an overall satisfaction will be descriptively summarized by treatment and visit.

7. SAFETY ANALYSIS

The SAF will be used for all safety analyses unless noted otherwise. Safety will be assessed on the basis of AE reports, clinical laboratory data, physical examinations, vital signs, orthostatic blood pressure (Part 1 only), post-void residual volume, urodynamics assessments (Urodynamics substudy only), and prostate volume measurement.

7.1. Adverse Events

AEs will be coded using MedDRA version 22.0 or later.

All reported AEs (whether treatment emergent or not) will be included in by-subject AE listings. Sorting will be by country, site, subject, date of event, SOC, PT and then verbatim description.

An AE will be considered treatment emergent (TEAE) if it begins or worsens in severity after the first dose of the double-blind Study Treatment through 5 days after the last dose of Study Treatment or rollover to the extension study, whichever occurs first. Partial AE start dates will be imputed as detailed in [Section 4.2.3](#).

Summary tables will be based on TEAEs. The incidence of TEAEs will be presented using counts and percentages of subjects with TEAEs and tabulated by SOC and PT. SOC will be sorted in descending frequency and PT within SOC will be sorted by descending frequency based on the incidence across subjects overall. If a subject has multiple occurrences (start and stop) of an event associated with a specific SOC or PT within a SOC, a subject will only be counted once in the incidence count for the SOC or PT within SOC respectively.

An overall summary table of AEs by treatment group will be presented detailing the number and percentage of subjects, and number of events for the following categories:

- At least one TEAE;
- At least one Treatment-Related TEAE;
- At least one Grade ≥ 3 TEAE (Mild = Grade 1, Moderate = Grade 2, Severe or Medically Significant = Grade 3, Life-Threatening = Grade 4, Death = Grade 5)
- At least one Grade ≥ 3 Treatment-Related TEAE;
- At least one Serious TEAE;
- At least one Serious Treatment-Related TEAE;
- At least one TEAE leading to Discontinuation from Study Medication;
- At least one TEAE of Special Interest;
- At least one Treatment-Related TEAE of Special Interest

Where not otherwise noted, all the following summaries are presented by PT in descending overall frequency:

- All TEAEs (by SOC and PT in descending overall frequency);
- All TEAEs (by PT in descending overall frequency)
- Treatment-Related TEAEs (i.e., possibly or probably related);
- All TEAEs by SOC, PT, and maximum severity (where the maximum intensity per patient will be counted at each level of summarization);
- TEAES with Grade ≥ 3 ;
- Treatment-Related TEAES with Grade ≥ 3 ;

- Serious TEAEs;
- Treatment-Related Serious TEAEs;
- Fatal TEAEs;
- TEAEs leading to Discontinuation from Study Treatment;
- TEAE of Special Interest;
- Treatment-Related TEAE of Special Interest;
- Non-fatal TEAEs;
- Hypertension TEAEs by Pre-existing Hypertension (Yes vs No) and Baseline Hypertension (Yes vs. No). Hypertension TEAEs will be selected as any TEAE with preferred term of Hypertension.
- Non-serious TEAEs occurring in 2% or more of any treatment group.

In addition, a summary of all TEAEs by PT occurring in at least 2% of subjects in the vibegron arm and greater than the placebo arm will be created and sorted by descending frequency in the vibegron arm.

Adverse events of special interest for this study include:

- Adverse events consistent with urinary retention
- Adverse events suggestive of cystitis or urinary tract infection (UTI)
- Potential major cardiac and cerebrovascular events, including death (or any event with fatal outcome), myocardial infarction, cerebrovascular accident, hospitalization for unstable angina or chest pain, hospitalization for heart failure requiring hospitalization, and coronary revascularization/angioplasty/stent
- Adverse events consistent with hypertension (see protocol section 8.4.6)
- Elevated serum aspartate aminotransferase (AST) or alanine aminotransferase (ALT) lab value requiring that study drug be temporarily withheld or permanently discontinued
- Neoplasms

Treatment listings will include the treatment arm, start and stop dates of the AE, and days on study relative to the day of first dose of study treatment. A Treatment related AE is defined as an AE for which the investigator classifies the AE as being “Probably Related” or “Possibly Related” to study treatment on Adverse Event CRF. Missing relationship and severity (intensity) will be imputed per Section 4.2.3.

The following additional listings will be provided:

- Listing of deaths
- Listing of Serious TEAEs

- Listing of treatment-emergent AESIs
- Listing of TEAEs leading to withdrawal or Interruption of study treatment

Listing of all AEs with a flag for TEAEs and onset (Prior = prior to first dose of single-blind medication, Run-in = on or after first dose of single-blind medication but prior to first dose of double-blind medication, or Treatment = on or after first dose of double-blind medication.)

A listing of all medical history and pre-double-blind treatment adverse events with coded preferred terms belonging to the standard MedDRA query of hypertension will be created.

7.2. **Laboratory Evaluations**

All continuous laboratory parameters will be summarized descriptively by absolute value at each visit by treatment group, together with the corresponding changes from baseline. All parameters will be summarized in SI units.

The number and percentage of subjects with laboratory measurements outside of the central laboratory normal range will also be summarized by treatment group and visit. Shift tables from baseline to maximum post-baseline value, to minimum post-baseline value, last post-baseline value, and at each post-baseline visit will be provided for hematology and chemistry parameters to display low, normal, high, and missing values by treatment group in a 3-by-3 contingency table. Denominators for percentages will be the number of subjects with non-missing data at the specific assessment and baseline.

Maximum post-baseline total bilirubin will be presented (<2 and $\geq 2 \times$ ULN) and plotted against maximum post-baseline ALT (<3 , ≥ 3 - <5 , ≥ 5 - <10 , and $\geq 10 \times$ ULN), expressed as multiples of ULN. This will be repeated to show maximum post-baseline total bilirubin against maximum post-baseline AST.

Data for subjects with ALT or AST $\geq 3 \times$ ULN, and bilirubin $\geq 2 \times$ ULN will be presented, which will include all visits for this subset of subjects. A line plot of liver biochemistry test results (including ALP, ALT, AST, total bilirubin, and GGT) over time will also be presented for this subset of patients.

A sample for the urinalysis and urine culture will be sent to the central laboratory only if the urine dipstick performed at the site tests positive for the presence of leukocytes, nitrites, or blood cells. Dipstick results and central urinalysis data will be provided only in the listing.

Any data outside the central laboratory normal reference ranges will be explicitly noted on the listings that are produced.

7.3. **Vital Sign Assessments**

7.3.1. **Height, Weight, and Sitting Vital Signs**

Vital sign data including systolic and diastolic blood pressure, pulse rate, respiration rate, body temperature and weight will be collected at all study visits except for the safety follow-up visit. Height will be measured at Screening only. Blood pressure will be measured in triplicate at each

visit. The average of triplicates will be used for summary; if fewer than three measurements were collected the average of available measurements will be used. For subjects in Study Part 1 and visits with orthostatic blood pressure assessments, blood pressure (in triplicate) and pulse rate taken pre-dose in sitting position are equivalent to pre-dose regular vital sign values and will be used.

Vital signs will be summarized using absolute value and change from baseline. A summary by-visit according to the visit window rule in [Section 4.2.4.2](#), the maximum, and last post-baseline observation for each subject will be summarized for each of the vital signs. For change from baseline in blood pressure and pulse rate, least squares mean estimates and 95% CIs as described in section 4.2.2 will be presented from an ANCOVA model including terms for treatment, age, baseline parameter value, and pre-existing hypertension (Yes vs. No).

The line plot of mean (SE) of change from baseline in blood pressure and pulse rate over time will be prepared. A by-subject listing, sorted by subject identifier, will be presented including all vital sign results (scheduled or unscheduled).

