8.4.3. Follow-up of Adverse Events and Serious Adverse Events

After the initial AE or SAE report, the investigator is required to proactively follow each subject at subsequent visits/contacts. All AEs will be followed until the Safety Follow-up telephone call (5 days [\pm up to 2 days] after the last dose of study drug). All SAEs will be followed until resolution, stabilization, the event is otherwise explained, or the subject is lost to follow-up (as defined in [Section 7.3](#)). If a subject dies during participation in the study or within 5 days of the last dose of study drug, the investigator will provide the Sponsor or designee with a copy of any postmortem findings including histopathology.

The investigator is obligated to perform or arrange for the conduct of supplemental measurements and/or evaluations as medically indicated or as requested by the Sponsor or designee to elucidate the nature and/or causality of the AE or SAE as fully as possible. This may include additional laboratory tests or investigations, histopathological examinations, or consultation with other health care professionals.

New or updated information will be recorded in the originally completed eCRF. As noted above, the investigator will submit any updated SAE data to the Sponsor or designee within 24 hours of receipt of the information.

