9.4.3.1. Adverse Events

An AE will be considered a treatment-emergent AE (TEAE) if:

- The AE began on or after the date of the first dose of study drug; or

- The AE was present before the date of the first dose of study drug, but increased in severity or became serious on or after the date of the first dose of study drug

An AE that occurs more than 5 days after the last dose of study drug will not be counted as a TEAE.

An AE will be considered a treatment-emergent SAE (TESAE) if it is a TEAE that additionally meets any SAE criteria.

AEs will be coded using the latest version of MedDRA. An overall summary table of AEs by treatment group will be presented with number and percentage of subjects. The incidence of all TEAEs by primary SOC and PT will be prepared for all TEAEs, TESAEs, treatment-related TEAEs/TESAEs, TEAEs leading to discontinuation from study treatment and all TEAEs by maximum intensity. All AEs will be listed. The number and percentage of subjects with AEs of special interest, as defined in [Section 8.4.6](#), will be summarized by treatment group.

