- A discharge summary should be provided for all hospitalizations. If the subject died, the report should include the cause of death as the event term (with death as the outcome) and whether the event leading to death was related to study drug, as well as the autopsy findings, if available
- Nonserious AESIs should be reported on the eCRF within 72 hours of knowledge of the information.
- It is **not** acceptable for the investigator to send photocopies of the subject's medical records to the Sponsor or designee in lieu of completion of the AE or SAE eCRF page.
- There may be instances when copies of medical records for certain cases are requested by the Sponsor or designee. In this case, all subject identifiers, with the exception of the subject number, will be redacted on the copies of the medical records before submission to the Sponsor.
- The investigator will attempt to establish a diagnosis of the event based on signs, symptoms, and/or other clinical information. Whenever possible, the diagnosis (not the individual signs/symptoms) will be documented as the AE/SAE.

Assessment of Intensity

1/MILD	Asymptomatic or mild symptoms, clinical or diagnostic observations only; intervention not indicated.
2/MODERATE	Minimal, local, or noninvasive intervention indicated; limiting age-appropriate instrumental activities of daily living
3/SEVERE OR MEDICALLY SIGNIFICANT	Not immediately life-threatening; hospitalization or prolongation of hospitalization indicated; disabling; limiting self-care activities of daily living
4/LIFE-THREATENING	Life threatening consequences; urgent intervention indicated
5/DEATH	Death related to adverse event

An event is defined as *serious* when it meets at least one of the predefined outcomes as described in the definition of an SAE, NOT when it is rated as severe.

Assessment of Causality

- The investigator is obligated to assess the relationship between study drug and each occurrence of each AE or SAE.
- A *reasonable possibility* of a relationship conveys that there are facts, evidence, and/or arguments to suggest a causal relationship, rather than a relationship cannot be ruled out.
- The investigator will use clinical judgment to determine the relationship.
- Alternative causes, such as underlying disease(s), concomitant therapy, and other risk factors, as well as the temporal relationship of the event to study drug administration will be considered and investigated.

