4.2.4. Assessment Windows

4.2.4.1. Study Reporting Periods

Based on study design and variables under consideration, study time periods are defined as below.

Table 2: Definition of Study Reporting Periods

Analysis description	Analyzing Study Period	Start Date	End Date
General	Screening	Date of informed consent	Date of first run-in dose
	Run-in	Date of first run-in single-blind dose	Date of last run-in single-blind dose
	Treatment (Day 1 – Week 24)	Date of first double-blind dose	Date of last double-blind dose + 5 days
	Follow-up (up to Week 27)	>Date of last dose + 5 days	Date of EOS visit
Adverse events (based on AE start date)	Prior	Date of informed consent	Date of first run-in dose
	Run-in	Date of first single-blind run-in dose	Date of first double-blind dose
	TEAE	Date of first double-blind dose*	Date of last dose + 5 days
	Post-Treatment	Date of last dose + 5 days	N/A
Concomitant Medication/Procedure (any overlap with period)	Prior medication/procedure	N/A	Date of first double-blind dose

Analysis description	Analyzing Study Period	Start Date	End Date
	Concomitant medication/ procedure	Date of first double-blind dose	Date of last double-blind dose + 5 days
	Post medication/ procedure	>Date of last double-blind dose + 5 days	N/A
EOS: End of study is defined as the date when the subject has completed one of the following: completes Week 24 Visit for subjects who enroll into Study URO-901-3006 or Safety Follow-up for subjects who do not enroll into Study URO-901-3006, discontinued from the study, or is lost to follow-up.			

*AEs with a start date equal to the date of first double-blind dose will be considered treatment-emergent unless the relatedness to study drug is marked 'Not applicable'.
 
Overlapping period: Medication start date<= period start date<medication end date, medication start date<period end date<=medication end date, or period start date<=medication start or end date<period end date, then the medication is considered overlapping with the period.
			

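### SAP 7.1 drops the protocol's seriousness criterion from the TEAE definition without declaring it, so a pre-dose event that becomes serious at an unchanged grade is not counted as a serious TEAE

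*SAP*

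**What the plan says.** Protocol 9.4.3.1 gives two routes to treatment-emergent status. One is onset on or after the date of first dose. The other is for an event present earlier that "increased in severity or became serious on or after the date of the first dose of study drug". It then builds the serious category on top: "An AE will be considered a treatment-emergent SAE (TESAE) if it is a TEAE that additionally meets any SAE criteria".

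SAP 7.1 makes an event treatment-emergent "if it begins or worsens in severity after the first dose of the double-blind Study Treatment", up to 5 days after the last dose or rollover to the extension study. Seriousness is not mentioned. The same section states that "Summary tables will be based on TEAEs", and the overall summary includes a row for "At least one Serious TEAE". SAP Table 9 plans a table of serious TEAEs, a table of treatment-related serious TEAEs and a listing of treatment-emergent SAEs.

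SAP Table 2 (Section 4.2.4.1) also defines a TEAE period. Its row is labelled "Adverse events (based on AE start date", and it runs from the first double-blind dose to 5 days after the last dose.

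SAP Section 9 declares changes on three topics: exploratory endpoints, the responder analysis and COVID-19. Neither that section nor the SAP version history mentions the TEAE definition.

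**The concern.** The two definitions differ in current text, and the difference touches a safety count that readers of the study report will rely on. Under Protocol 8.4.1, events are collected from consent, and screening can start as early as Day -49, so some events may be ongoing at the first double-blind dose. If one of them becomes serious on treatment at an unchanged grade, the protocol counts it as a treatment-emergent SAE and the SAP does not.

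With everything else equal, removing a criterion can only lower the number of serious TEAEs. The SAP plans no separate table of all SAEs that would bring such an event back into a count. Because the change is undeclared, a reader comparing the report with the protocol would not know that the rule had moved.

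**Working it through.** There is no figure to reproduce. The check sets the texts side by side and follows one event through them.

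**Test event:** onset in screening or run-in at some grade, not serious, ongoing at the first double-blind dose; it becomes serious during treatment and stays at the same grade.

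| Rule | Began on treatment? | Worsened in severity? | Became serious? | Result |
|---|---|---|---|---|
| Protocol 9.4.3.1 | No | No | Yes, and it counts | TEAE and treatment-emergent SAE |
| SAP 7.1 | No | No | Not a criterion | Not a TEAE |
| SAP Table 2 | No | Not a criterion | Not a criterion | Not a TEAE |

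**Could the severity clause pick the event up?** Not for this test event. Protocol Appendix 3 (Section 10.3, Assessment of Intensity) defines seriousness by outcome, "NOT when it is rated as severe". Seriousness can also change with no necessary change in grade. The appendix treats at least 24 hours of emergency-room observation as hospitalization, tells sites to treat doubtful cases as serious, and makes important medical events serious by judgment.

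**Could a new onset date pick it up?** No. Protocol 8.4.3 says: "New or updated information will be recorded in the originally completed eCRF". The event keeps its pre-dose onset.

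**How wide is the gap?** Compare the seriousness criteria with the grading scale in the same appendix:

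- Death corresponds to Grade 5.
- Life-threatening corresponds to Grade 4.
- Hospitalization corresponds to Grade 3.
- Disability corresponds to the disabling wording in Grade 3.
- Important medical events overlap with the medically significant label of Grade 3.
- Congenital anomaly has no matching grade, but is not a way for a participant's own ongoing event to become serious.

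A Grade 1 or 2 event that becomes serious would therefore often be regraded, and would then meet the SAP's worsening clause. What remains is mainly (a) an event already at Grade 3 or above, not serious and ongoing before dosing in a man who is still randomized, and (b) an event marked serious without being regraded.

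**Where would the event still appear?** In the by-subject listing of all adverse events (SAP 7.1), in the screening or run-in listing (SAP Table 11), and in the deaths listing if fatal. It would not appear in any TEAE table or in the listing of serious TEAEs.

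**Table 2.** By using onset alone, Table 2 also excludes a pre-dose event that worsens in severity, which SAP 7.1 includes. This mismatch is internal to the SAP, and it is wider than the omission in SAP 7.1.

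**The case against.** The strongest case on the other side has three parts.

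First, the grading scale does most of the work of the missing clause. This stands, and it limits the point. A reader might infer from the protocol's separation of serious and severe that the severity clause never captures an event that becomes serious. The documents do not support that: the statement says that a severe rating does not make an event serious, and the grade wording implies that many events that become serious also rise in grade.

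Second, nothing disappears from the record. All adverse events are listed with a TEAE flag, SAEs are reported within 24 hours whatever their TEAE status, and the DSMB reviews safety data throughout. This also stands, so it would be wrong to infer that serious events go unreported. But a listing does not put the event back into the serious TEAE counts.

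Third, Protocol 9.4.3 leaves the full definition of the safety analysis to the SAP. That permits elaboration. It does not cover the silent removal of a criterion that the next protocol section states explicitly, when SAP Section 9 exists to record departures and does record smaller ones, such as adding Week 24 to two exploratory scores.

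**Conclusion.** The mismatch is certain on the text; its practical effect is probably very small. Followed as written, the SAP leaves a same-grade event that becomes serious out of the serious TEAE row, tables and listing, contrary to the protocol's own rule. Efficacy results are not affected.

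Three further inferences are not supported:

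- **A count.** A reader might set the few weeks of pre-dose collection against 24 weeks of treatment and conclude that only a handful of events are at stake. The documents give no rates, and the lengths of the periods do not bound the number of events that are ongoing at first dose and later become serious.
- **A bias toward one arm.** The omission can lower the count in either arm; nothing in the documents says which.
- **That Table 2 follows from the dropped clause.** It leaves out worsening as well, and needs correcting in its own right.

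The conclusion assumes that the protocol's first dose of study drug means the first double-blind dose, as in the SAP. The protocol also uses that term for run-in placebo. On that literal reading, run-in onsets would already be TEAEs under the protocol, which would widen the difference from the SAP.

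**What to change.** 1. In SAP 7.1, restore the second trigger for events present before dosing: the event becomes serious on or after the date of the first double-blind dose.
2. Separately, align SAP Table 2 with SAP 7.1, so that TEAE status rests on onset, worsening in severity or becoming serious, and not on start date alone.
3. If the omission was intended, declare and justify it in SAP Section 9. If the SAP is already final, SAP Section 1 sends changes to the clinical study report.

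The text change is one clause in SAP 7.1 and a note to Table 2. The real cost is in programming: the date on which an ongoing event became serious must be derivable from the AE/SAE record. The documents describe no dedicated field for it, so this should be confirmed before the rule is finalized. The existing worsening clause already needs a dated change in severity, so the requirement is of a kind the SAP already carries.
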